### **Pharmacokinetic Analysis Set**

All participants with evaluable PK data will be included in the pharmacokinetic analysis set.

### **ITI treatment analysis population**

All participants who enter ITI treatment with study intervention will be included in the analysis for ITI treatment.

## **6. Statistical Methodology**

The statistical evaluation will be performed by using the software package SAS release 9.2 or higher (SAS Institute Inc., Cary, North Carolina, United States). All data will be listed and summary tables will be provided. The number of data available and missing data, mean, standard deviation, median, Q1-Q3, minimum and maximum summary statistics will be calculated for continuous data. Frequency tables will be generated for categorical data.

In safety evaluation (vital signs, and laboratory), the last non-missing pre-dose measurement before first study drug administration will be used as baseline.

### **6.1 Population characteristics**

#### **6.1.1 Demography and baseline characteristics**

Demographic characteristics, including age, weight, height, BMI will be presented for all subjects and by age groups (<12 or  $\geq$ 12 years of age) in Part A, and by all subjects in Part B in the form of summary statistics. Other baseline characteristics, including previous treatment characteristics, disease history, target joints, previous number of bleeds, laboratory findings and vital signs, will be handled similarly.

#### **6.1.2 Extent of exposure**

Extent of exposure to the study drug, including exposure days, number of days in the study, compliance, frequency of prophylaxis at start and end of study, infusion characteristics [i.e.

## Statistical Analysis Plan

BAY 81-8973 (KOVALTRY) / 19855

Page: 11 of 15

number of all infusions, total doses (all infusions), total dose per kg (all infusions), total dose per infusion etc. ] will be summarized for each subject receiving any amount of drug. In addition, extent of exposure for surgeries will be summarized separately.

Compliance of each patient will be calculated as below:

Prophylaxis infusion Compliance =  $100\% * \text{number of actual prophylaxis infusion} / \text{number of planned prescribed prophylaxis infusion}$  excluding the bleeding and surgery period

The bleeding and surgery period is defined as the first infusion for a bleed/surgery until next administered prophylaxis infusion.

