### **6.8.2 Temporary Discontinuation of Study Intervention**

Participants who have an emergency major surgery during the study may be treated with KOVALTRY or other FVIII, according to local practice at the discretion of investigators. Participants will resume their treatment assignment of KOVALTRY as per this protocol after surgical recovery. Duration of interruption of study intervention (i.e., prophylaxis treatment with KOVALTRY) should not be more than 2 weeks.

During the trial, it is expected that all reasonable attempts will be made to ensure that study participants will comply with and adhere to their prophylaxis infusion schedule with few interruptions. In rare instances, it may be necessary for a study participant to temporarily discontinue study intervention (e.g., difficulty with IV access in children, travel to locations where appropriate support for infusions is not available). Study participants/caregivers should inform the investigator of all such situations, and the reasons must be documented in the

medical record. Prolonged periods (>2 weeks) or repeated breaks in the prophylaxis schedule should be avoided and could result in the study participant being removed from the study.

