### Part A (PTPs)

Part A will assess the efficacy, safety, and PK of KOVALTRY in previously treated Chinese children and adolescents/adults with severe hemophilia A. Part A is planned to investigate a total of 42 PTPs (30 children and 12 adolescents/adults). PK will be assessed in a subset of 12 children (<12 years) and in 12 adolescents/adults ( $\geq 12$  years).

Efficacy and safety data for use of KOVALTRY for treatment of bleeding episodes will also be collected.

- Study participants will be treated for 6 months with the following dose regimen for prophylaxis according to the prescribing information for KOVALTRY:
  - Study participants  $\leq 12$  years of age: 25 to 50 IU of KOVALTRY per kg body weight twice weekly, three times weekly, or every other day according to individual requirements for 6 months.
  - Study participants  $> 12$  years: 20 to 40 IU of KOVALTRY per kg of body weight two or three times per week according to individual requirements for 6 months.
- Part A will include 5 study visits (Screening, Baseline, Visit 3/Month 1, Visit 4/ Month 2, Visit 5/Final study visit/Early Termination). All participants will also receive a safety follow-up call approximately 2 weeks after the final study visit.

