### 3.1 Sample size determination

#### 3.1.1 Part A (PTPs)

The primary variable “annualized bleeding rate (ABR)” is used for the evaluation of the efficacy. The mean ABR for total bleeding episodes for previously treated severe hemophilia A study participants < 12 year of age receiving prophylaxis with KOVALTRY in completed LEOPOLD Kids Part A study was  $3.75 \pm 4.98$  (median (Q1; Q3) 1.90 (0.00; 6.02). Assuming that the average ABR for this patient population is 4 bleeding episodes and the standard deviation is 5 bleeding episodes per year, a sample size of 30 participants will allow estimating ABR by means of a 95% confidence interval with a half-width of 1.8 (the confidence interval is (2.2-5.8) which will consider to provide reasonable precision on the estimations.

For the previously treated adult/adolescent treatment arm, the proposed sample size of 12 participants is adequate for collection of PK data and will also allow for collection of supplemental efficacy and safety data in this population.

The sample size (30 children + 12 adolescents and adults) has been confirmed in consultation with China CDE, as adequate to provide additional clinical data for comprehensive evaluation of efficacy, safety, and PK of KOVALTRY in Chinese hemophilia A patients.

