#### 4.2 Handling of Dropouts

Annualized number of total bleeds will be calculated for all subjects, including dropouts. Subjects who drop from the study will be included in a listing.

During the study, temporary discontinuation of study drug could happen, the duration of interruption of study intervention (i.e. prophylaxis treatment with KOVALTRY) should not be more than 2 weeks. Prolonged periods ( $> 2$  weeks) or repeated breaks in the prophylaxis schedule should be avoided and could result in the study participant treated as drop out, or being removed from the study.

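### Compliance can be overstated after treated bleeds or surgery, because the excluded period closes only when prophylaxis is actually resumed and has no cap

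*SAP*

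**What the plan says.** SAP 6.1.2 lists "compliance, frequency of prophylaxis at start and end of study" among the exposure summaries. The compliance percentage has actual prophylaxis infusions in the numerator and "number of planned prescribed prophylaxis infusion" in the denominator, "excluding the bleeding and surgery period". That period is then defined: "The bleeding and surgery period is defined as the first infusion for a bleed/surgery until next administered prophylaxis infusion".

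Two features of the definition matter. It opens at an infusion, so a bleed that is recorded but not treated (Protocol 7.3.1 records both kinds) opens no period. It closes at a prophylaxis dose that was given. Neither document sets a maximum length, says when prophylaxis counts as due again, or asks for a version without the exclusion.

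The plan does take gaps in prophylaxis seriously. Protocol 6.8.2 says: "Prolonged periods (>2 weeks) or repeated breaks in the prophylaxis schedule should be avoided". SAP 4.2 says that "the duration of interruption of study intervention (i.e. prophylaxis treatment with KOVALTRY) should not be more than 2 weeks".

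**The concern.** Leaving out planned doses that bleed treatment replaced is a reasonable aim. The difficulty is the open end. No prophylaxis is given inside the period before the dose that closes it. Every planned dose missed there is therefore removed from the denominator while the numerator stays the same. A participant whose only missed doses follow treated bleeds scores 100% however long each gap lasts, and if prophylaxis is never resumed the period has no defined end.

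The distortion is linked to the outcome, because only participants with treated bleeds or surgery have such periods, and more treated bleeds give more opportunity for it. At stake is how the ABR is read. Under SAP 4.5 the treatment period runs from first treatment to the later of last infusion and last visit, with only the optional immune tolerance induction period removed. Days and bleeds during a lapse stay in the ABR while the missed doses of the same days drop out of compliance. A reader could see a raised ABR beside full compliance and not consider missed doses as an explanation.

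**Working it through.** The documents state no compliance figure, threshold or worked example, so there is nothing of the plan's own to reproduce. The calculation below is an illustration.

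**Inputs from the documents**
- Part A regimens for children: "twice weekly, three times weekly, or every other day according to individual requirements for 6 months" (SAP section 3). Taking 6 months as 182 days gives 52, 78 and 91 planned doses.
- Number of bleeds: "Assuming that the average ABR for this patient population is 4 bleeding episodes" per year (SAP 3.1.1), so 4 × 0.5 = 2 in 6 months. This counts all bleeds; treated bleeds may be fewer.
- Longest gap illustrated: 2 weeks, the limit in SAP 4.2.
- Treatment days for a bleed: 4, the upper stated number in the moderate-bleed row of Protocol Table 10–3, though that row allows longer. It is used only to bound a comparison window.

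**Assumptions**
- The first infusion for each bleed falls the day after a planned dose.
- Prophylaxis restarts at the first planned dose after the gap.
- No other dose is missed.
- The closing dose is counted in both numerator and denominator.

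**Formulas**, with P = planned doses, M = planned doses missed in the gaps, and T = those of M that fall within the 4 treatment days:
- SAP rule: (P − M) / (P − M)
- Only treatment days excluded: (P − M) / (P − T)
- No exclusion: (P − M) / P

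**Two treated bleeds**

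| Regimen | Gap after each | P | M | T | SAP rule | 4-day window | No exclusion |
|---|---|---|---|---|---|---|---|
| Twice weekly | 2 weeks | 52 | 8 | 2 | 44/44 = 100% | 44/50 = 88.0% | 44/52 = 84.6% |
| Three times weekly | 2 weeks | 78 | 12 | 4 | 66/66 = 100% | 66/74 = 89.2% | 66/78 = 84.6% |
| Every other day | 2 weeks | 91 | 14 | 4 | 77/77 = 100% | 77/87 = 88.5% | 77/91 = 84.6% |
| Twice weekly | 1 week | 52 | 4 | 2 | 48/48 = 100% | 48/50 = 96.0% | 48/52 = 92.3% |
| Three times weekly | 1 week | 78 | 6 | 4 | 72/72 = 100% | 72/74 = 97.3% | 72/78 = 92.3% |

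**Range against the 4-day window**
- Prophylaxis resumes at the first planned dose after treatment ends: M = T, so the difference is 0 points.
- One bleed with a 2-week gap, twice weekly: 48/51 = 94.1%, a difference of 5.9 points.
- Four bleeds with 2-week gaps, twice weekly: 36/48 = 75.0%, a difference of 25 points. This is the extreme of the cases examined.

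**Same behaviour without a bleed.** At three times weekly, 12 missed doses with no preceding treated bleed score 66/78 = 84.6%. The same 12 after two treated bleeds score 100%.

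**Closing dose.** The SAP does not say whether the dose that ends the period lies inside it. If it is removed from the denominator but kept in the numerator, the twice-weekly two-bleed case becomes 44/(52 − 8 − 2) = 44/42 = 104.8%.

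**ABR beside it.** Two 2-week gaps are about 28 of 182 days, or 15.4% of the ABR denominator, in a participant reported as 100% compliant.

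**The case against.** The best case against the point is that no stated analysis depends on this percentage. The study is descriptive (SAP 4.1). The ABR formula uses days in the treatment period (SAP 4.5). The per-protocol set rests on completion, 50 exposure days and important deviations settled at validity review (SAP 5.1), with no compliance threshold. All of that stands and limits the point to a minor one.

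A reader might infer that breaks in prophylaxis would go unnoticed as deviations. The documents do not support that. Breaks come to light through vial return and diary review (Protocol 6.4), calls about every 2 weeks (Protocol 1.3.1), the duty to report interruptions (Protocol 6.8.2) and validity review (SAP 4.6). Exposure days and infusion counts are also summarized. In the twice-weekly two-gap case 44 prophylaxis infusions remain, which is below the 50-exposure-day criterion unless bleed treatment adds at least 6 exposure days. These figures do not, however, show the shortfall against the prescribed schedule, which is what the compliance percentage is for.

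A reader might also infer that all time after any bleed is excluded, or that compliance is always overstated. Neither follows. Untreated bleeds exclude nothing, and timely resumption gives no bias. Nor does a gap imply a choice by the participant: Protocol 6.8.2 provides for resuming after surgical recovery.

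It can be said that an observed infusion is easier to program than a due date, since regimens are stated as times per week and can change. This carries little weight, because the formula already needs a count of planned doses outside the period. Finally, SAP section 1 refers to separate dataset specifications that are not available here. A cap could be written there, but the SAP text does not point to one.

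**Conclusion.** The point holds as a minor flaw in the definition. As written, planned prophylaxis doses missed after bleed or surgery treatment has ended leave the denominator without limit, so compliance can be overstated in participants with treated bleeds or surgery.

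The size rests on gap lengths that the documents do not give. It is nil when prophylaxis resumes on schedule and about 11 to 12 points for two treated bleeds each followed by 2 weeks without prophylaxis, judged against a 4-day treatment window. That 2-week gap is the outer limit the plan tolerates, not an expected value. The lower figure of 85% in the same example arises only if no dose at all is excluded, which is stricter than the SAP's reasonable aim.

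The documents do not support a claim that the primary endpoint, the stated per-protocol criteria or the detection of deviations is compromised. What is affected is the interpretation of ABR beside the reported compliance.

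**What to change.** This is a change to the analysis only, in SAP 6.1.2:

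- End the excluded period at the first prophylaxis dose planned after the last infusion for the bleed or surgery (or after documented surgical recovery), or at the next prophylaxis infusion given if that is earlier. Count later unmet planned doses as missed.
- State that planned dates come from the regimen prescribed at the time, so that a change of frequency is handled the same way for everyone.
- State that the closing dose is counted in both numerator and denominator.
- Report compliance without any exclusion alongside.

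The cost is a sentence or two in the SAP and a small programming change, with no new data collection. The downside is that reported compliance may be lower.

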### 6.2 Efficacy

All efficacy analyses will be performed on the mITT population. In case more than 5% of participants in one arm (children or adolescents/adults) are excluded from the mITT population, the analyses for primary and secondary endpoints will be repeated in the PP population.

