**Table 9–1: Analysis Populations**

Population	Description
Enrolled	All participants who signed the ICF or had an ICF signed on their behalf by a parent or legal representative.
Safety	Participants enrolled into the study and received at least 1 dose of study drug. The safety population will be used for the safety analysis.
Modified Intent-to-Treat (mITT)*	All study participants who have infusion/bleeding data from the EPD and/or CRF. The mITT population will be used for the efficacy analysis.
Per Protocol (PP)**	All mITT participants who completed study treatment and have at least 50 exposure days on study, without major protocol deviations.
PK analysis population	All participants with evaluable PK data will be included in the analysis of pharmacokinetic data.
ITI treatment analysis population	All participants who enter ITI treatment with study intervention will be included in the analysis for ITI treatment.

\* The ITT is inclusive of all enrolled and eligible patients. Modified ITT was introduced for this study as there is an additional condition that is to be met for participants included in ITT. This condition is that study participants need to have infusion/bleeding data from the EPD and /or CRF.

Therefore, ITT analysis population is renamed “modified ITT” for this study.

\*\* Only to be used if at least 5% of mITT participants (<12 or ≥12 years of age) are excluded from the PP population. The PP population is only in Part A; Part B will not have a PP population.

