#### **9.4.2 Primary Endpoint(s)**

All efficacy analyses will be performed on the mITT population. In case of PP population (Part A only), more than 5% of participants in one arm (children or adolescents/adults) are excluded from the mITT population, and analyses for primary and secondary endpoints will be repeated in the PP population. As the non-adherence to the EPD documentation is considered independent from the treatment efficacy, the exclusion of participants without bleeding/infusion data from the EPD does not interfere with the intention-to-treat principle. These participants are excluded in order not to dilute the treatment effect.

The primary endpoint in Part A is the ABR of all bleeding episodes during prophylaxis treatment, and it will be summarized by age group (<12 y, ≥12 y) separately.

The primary endpoint in Part B is the ABR of all bleeding episodes within 48 hours of a previous prophylaxis infusion.

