#### Enrolled population

All participants who signed the ICF or had an ICF signed on their behalf by a parent or legal representative

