#### Modified Intent-To-Treat (mITT)

All study participants who have infusion/bleeding data from the EPD and/or CRF will be included in mITT. The mITT population will be used for the efficacy analysis.

The ITT is inclusive of all enrolled and eligible patients. Modified ITT was introduced for this study as there is an additional condition that is to be met for participants included in ITT. This

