### **Per protocol set (PPS)**

All mITT participants, who completed study treatment and have at least 50 exposure days on study, without important protocol deviations significantly impacting efficacy endpoints will be included in PPS. The detailed definitions and the assignment of subjects to this analysis set will be based on the validity review meeting.

The PPS population will only be used for the efficacy analysis if at least 5% of mITT participants (<12 or  $\geq$ 12 years of age) are excluded. The PP population is only in Part A; Part B will not have a PP population.

Exposure days refers to days with at least one infusion of study drug.

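### The Part A per-protocol repeat has two incompatible triggers: SAP 6.2 and protocol 9.4.2 count exclusions from the mITT set, while protocol Table 9-1 and SAP 5.1 count mITT participants excluded from the per-protocol set

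*SAP*

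**What the plan says.** Four places set the condition for using the per-protocol set in Part A.

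- Protocol Table 9-1, footnote: "Only to be used if at least 5% of mITT participants (<12 or ≥12 years of age) are excluded from the PP population".
- SAP 5.1, Per protocol set: "The PPS population will only be used for the efficacy analysis if at least 5% of mITT participants" in either age group are excluded. The sentence does not name the set they are excluded from, but it stands in the PPS definition, so the PPS is meant.
- SAP 6.2: the primary and secondary endpoint analyses are repeated in the per-protocol population "In case more than 5% of participants in one arm (children or adolescents/adults) are excluded from the mITT population".
- Protocol 9.4.2: the condition is "more than 5% of participants in one arm (children or adolescents/adults) are excluded from the mITT population". It sits in a sentence that opens with a reference to the PP population and does not parse cleanly.

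The two sets have very different entry conditions. For mITT, SAP 5.1 says: "All study participants who have infusion/bleeding data from the EPD and/or CRF will be included in mITT". The PPS is the part of mITT "who completed study treatment and have at least 50 exposure days on study" and without important deviations that affect efficacy.

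**The concern.** The first two places measure how many analysed participants fail the per-protocol conditions. The other two, as written, measure how many participants never enter the efficacy analysis at all. Only the first quantity bears on whether a per-protocol repeat is informative.

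The repeat is the only analysis in either document that shows whether the primary and secondary efficacy results hold up once non-completers, participants with low exposure and participants with important deviations are removed. A programmer working from SAP 6.2 could properly skip it in a trial where well over 5% of an age group is outside the PPS.

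Timing adds to this. Protocol Section 9 relies on an early final SAP to limit the risk of an open-label design. SAP 4.6 and 5.1 leave assignment to the PPS to a review of study data. With two triggers on paper, the choice of which one applies would be made at that same review, with open-label data in view.

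**Working it through.** No figure in the plan is to be reproduced here. The check applies each trigger to the planned Part A groups.

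**Inputs**
- Group sizes: 30 children and 12 adolescents/adults (SAP Section 3, Part A).
- The first Part A dose is given at the study center (protocol 7.1.2).
- Recovery is measured in all Part A participants around an in-hospital infusion at Visit 2 (protocol 7.3.2).
- Infusions at protocol-mandated visits are recorded on CRF pages (protocol 7.3.1).
- Infusion data in the CRF alone are enough for mITT (SAP 5.1).

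**Step 1: counts needed.** 5% of 30 is 1.5 and 5% of 12 is 0.6. 'More than 5%' and 'at least 5%' therefore both need 2 children (2/30 = 6.7%) or 1 adolescent/adult (1/12 = 8.3%). One child (1/30 = 3.3%) is not enough. The difference in inequality changes nothing at the planned sizes; the real conflict is the set that is named.

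**Step 2: expected exclusions from mITT.** From the inputs, each dosed participant should have at least the Visit 2 infusion on the CRF. With complete records, 0 of 42 dosed participants fall outside mITT.

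**Step 3: the two rules side by side, dosed participants as base**

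| Outside the PPS | Outside mITT | Table 9-1 / SAP 5.1 | SAP 6.2, literal |
|---|---|---|---|
| 1 of 30 children (3.3%) | 0 | not met | not met |
| 2 of 30 children (6.7%) | 0 | met | not met |
| 1 of 12 adolescents/adults (8.3%) | 0 | met | not met |

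**Step 4: how often the rules would differ.** Assume each participant falls outside the PPS independently with the same probability p. The documents give no value, so a range is shown. Under Table 9-1 the chance that at least one age group meets the trigger is 1 − (1 − P_c)(1 − P_a). Here P_c = P(X ≥ 2) for X binomial (30, p), and P_a = 1 − (1 − p)^12.

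| p | P_c | P_a | Either group |
|---|---|---|---|
| 1% | 0.036 | 0.114 | 0.146 |
| 2% | 0.121 | 0.215 | 0.310 |
| 5% | 0.446 | 0.460 | 0.701 |
| 10% | 0.816 | 0.718 | 0.948 |

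At p = 5%: 1 − (0.554 × 0.540) = 0.701. Under the literal SAP 6.2 rule, with complete CRF records, the corresponding chance is 0 at every p.

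**Step 5: are exclusions from the PPS plausible?** Six months is 365.25/2 = 182.6 days. Twice-weekly prophylaxis gives 182.6/7 × 2 = 52.2 exposure days, and 52.2 × 0.95 = 49.6 at 95% adherence, against a threshold of 50. Infusions for bleeds add days, so this is a guide only. In the pediatric study described in the package insert (protocol Section 12), 9 + 13 = 22 of 51 children started on a twice-weekly regimen. Exposure days ranged from 37 to 103, with over 95% of prescribed infusions given. Some participants missing the 50-day condition is therefore foreseeable.

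**The case against.** The strongest reply is that the intended rule is already on paper. Table 9-1 states it fully, SAP 5.1 states it by context, and nothing says that SAP 6.2 overrides SAP 5.1. This stands. A reader might infer from SAP 6.2 that the plan as a whole can never run the per-protocol analysis. The documents do not support that, because two of the four places give a workable rule. The defect is a contradiction.

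A reader might also infer the opposite: since "All participants who signed the ICF or had an ICF signed on their behalf by a parent or legal representative" count as enrolled, screen failures would be excluded from mITT and the trigger would always fire. That does not hold up either. Table 9-1 and SAP 5.1 derive mITT from an ITT set limited to participants who are eligible as well as enrolled, so screen failures sit outside the natural base. The synopsis figures of about 50 screened for 42 evaluable do not settle it, because 'evaluable' is not defined. Nor is there harm in a repeat when nobody is excluded: the PPS would then equal mITT and give identical results.

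It can further be said that protocol 9.4.2 means 'removed from mITT to form the PP set', given how its sentence opens. That reading is possible but weak. The sentences that follow defend leaving out participants who lack diary data, which is exclusion from mITT. SAP 6.2 has no such opening words. Those same sentences show that the protocol contemplates some mITT exclusions, so 'not expected to fire' is safer than 'cannot fire'. Even then, the condition would be responding to missing diary data and not to adherence.

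Finally, the study is descriptive and tests no hypothesis. This is right, and it limits the weight of the point.

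**Conclusion.** The contradiction is real, and SAP 6.2 is wrong as written; the consequence is minor. Followed literally, SAP 6.2 would be expected to skip the per-protocol repeat in cases where Table 9-1 requires it, starting at 2 of 30 children or 1 of 12 adolescents/adults outside the PPS. The primary mITT result does not change. What is at stake is whether the one planned sensitivity analysis for non-adherence, non-completion and low exposure is run.

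This rests on three things: the planned group sizes, complete CRF records of the Visit 2 infusion, and the SAP 5.1 definition under which CRF data alone admit a participant to mITT. The probabilities in the working also assume independent exclusions with a common p; the contradiction itself does not depend on them.

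**What to change.** In SAP 6.2 and protocol 9.4.2, replace the condition with the Table 9-1 rule, for example: *If at least 5% of mITT participants in an age group (<12 or ≥12 years) are excluded from the PPS, the primary and secondary efficacy analyses will be repeated in the PPS.* Complete the SAP 5.1 sentence by naming the PPS as the set from which participants are excluded, and use 'at least 5%' in all four places.

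The cost is one sentence in each document, a few words in SAP 5.1, and at most one additional set of tables. SAP version 2.0 is based on protocol version 2.0 while the protocol now stands at version 4.0, so the change can go into an alignment update. It should be made before the data review that assigns participants to analysis sets.
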